### Exclusion criteria for men only:

- 1. Having a residual urine volume >150 cc by ultrasound or catheter.
- 2. Currently being treated for chronic bacterial prostatitis as documented by a positive urine culture.
- 3. History of prostate cancer.

### Exclusion criteria for women only:

1. Currently pregnant or breastfeeding.

### 6.2.3 Deferral Criteria

There are several physical conditions for which a participant will be deferred from entry into the ICCTG Study. Once it is formally ascertained that the condition is not present or has subsided according to the time frame identified, the participant will be reconsidered for entry into the ICCTG Study. The following list identifies the conditions for deferment and the criteria that a participant must meet in order to be evaluated further for entry into the study:

- 1. If a participant has initiated any new medications for IC during the past 4 weeks, he/she will be deferred until he/she has been on the same dose for at least 4 weeks.
- 2. Within six weeks prior to study enrollment, if a participant has undergone bladder instrumentation such as urethral dilation, urodynamics, bladder cystoscopy or

- bladder biopsy under general or regional anesthesia, he/she will be deferred until at least 6 weeks from the date of the procedure.
  - 3. If a participant has undergone hydrodistention within six weeks prior to study enrollment, he/she will be deferred until at least 12 weeks from the date of the procedure.
  - 4. If a participant has had a positive urine culture (100,000 col.ct) during the past 6 weeks, he/she will be deferred until the participant has been without the condition for at least 6 weeks.
  - 5. Participating in another intervention study or received an investigational drug or device within 4 weeks prior to screening.
  - 6. If a participant has active genital herpes or has had active genital herpes during the past 12 weeks, he/she will be deferred until the participant has been without the condition for at least 12 weeks.
  - 7. If a participant has had any intravesical treatment (i.e. DMSO, Heparin, cystostat) other than BCG within 12 weeks prior to study enrollment, he/she will be deferred until at least 12 weeks after the last treatment received.
  - 8. Participants treated with botulinum toxin injections for voiding dysfunction within 24 weeks prior to baseline will be deferred until 24 weeks after last treatment received.
  - 9. History of incontinence surgery or any other bladder or urethral surgery within the past 24 weeks, which could interfere with bladder function.
  - 10. Participants must have been off treatment with pentosan polysulfate (Elmiron®) for a minimum of four weeks prior to randomization.

### Deferral criteria for women only:

- 1. If a participant has active vaginitis, she will be deferred until she is free of the condition.
- 2. If a participant has had any form of transvaginal surgery, hysterectomy, prolapse surgery, vaginal delivery or C-section, she will be deferred until at least 24 weeks from the date of the procedure.
- 3. Participants must have completed breastfeeding for 24 weeks prior to study enrollment.

### Deferral criteria for men only:

1. Having had a TURP, TUIP, TUIBN, TUMT, TUNA, balloon dilation of the prostate, open prostatectomy or any other prostate treatment such as cryotherapy or thermal therapy, participant will be deferred until or at least 24 weeks from the date of the procedure.

### **7 Biomarkers Studies**

One of the major frustrations associated with IC is the lack of objective markers to diagnose and monitor disease progression. Recently, several urinary markers have been

identified; however, there are minimal data available regarding their utility in diagnosing IC and monitoring changes in the disease. Therefore, a component of this trial of intravesical BCG for the treatment of IC will involve collecting and processing urine specimens at defined intervals to study alterations in urine IC markers as a result of BCG and/or placebo therapy, and then correlate any alterations with changes in symptom scores at each defined time point to determine whether response to treatment is predictable. In addition, the same urine specimens will be used to measure other physiologic markers associated with known effects of BCG therapy, and to determine whether physiologic evidence of drug activity correlates with a change in symptom scores.

Urine specimens will be collected at four specific time points: immediately before administration of the first treatment, before the administration of the 4th treatment and six hours after the 4th treatment, and at the 34 week time point. The first pre-treatment, 4th pre-treatment, and 34 week specimens will be collected at the study sites, and cells removed by centrifugation. The cell pellet will be fixed using provided fixative and container for cytology. The urine will be separated into two sterile containers, one containing a stabilizing agent with a protease inhibitor tablet added for the chemokine/cytokine assays, and the other without preservative. (See Appendix E Urine Specimen Collection and Archive Protocol) The specimens obtained six hours after the 4th treatment will be collected at home by the patient, who will be given a cup and instructions for urine collection (See Appendix F Patient Instructions).

In order to investigate the potential impact of BCG on urine markers, the following markers will be considered for analysis:

- 1. Markers of IC: APF, HB-EGF, EGF, IL-6.
- 2. Markers of BCG activity: known markers for a Th1 or Th2 response, as well as control cytokines, IL-2, IL-8, IL-10, IFN-gamma, GMCSF, MCP-1 and IP-10.

In addition, urine cytology specimens will be evaluated for

- DNA cytometry and fluorescence in situ hybridization.
   Persistence of BCG (by PCR)

## **8 INVESTIGATIONAL MATERIAL**

## 8.1 TICE® Bacillus Calmette-Guérin [BCG (NSC-116327)]

 8.1.1 BCG Pharmaceutical Data:

Bacillus Calmette-Guérin is a freeze-dried lyophilized preparation of live mycobacteria containing 5±3 x 10^8 colony- forming units (CFU), per 50 mg (wet weight) of protein. This BCG is manufactured by Organon Teknika (Durham, NC) and is supplied in 2 mL glass vials. The package insert Appendix H.

### 8.1.2 BCG Storage and Stability:

Storage of the intact vials of TICE® BCG should be at refrigerated temperatures of 2-8 °C (36-46 °F). BCG contains live bacteria and should be protected from light. Do not freeze. BCG has limited stability after production. Check expiration date on vial. Use within two hours of reconstitution and discard any unused portion.

## 8.1.3 BCG Preparation of Agent:

Using aseptic methods, draw 1-mL of sterile, preservative-free saline into a small (3 mL) syringe and add to one vial of TICE® BCG to resuspend. Draw mixture into the syringe and gently expel into the vial until grossly observable particles are thoroughly dispersed to ensure thorough mixing. Dispense the BCG suspension into the tip end of a catheter-tip syringe that contains 49 mL preservative-free saline diluent bringing the total volume to 50 mL. To prevent clumping, exclude all air from the syringe. Gently rotate the syringe. The suspended TICE® BCG should be used immediately after preparation. Discard after two hours. See Appendix D for details on the **syringe masking procedure**.

### 8.1.4 BCG Dose:

The intravesical dose consists of one vial of 1 mL of TICE® BCG. This is then used to combine with 49 mL of preservative-free sterile saline. The intravesical dose will be 50 mL.

## 8.1.5 BCG Disposal and Clean-Up:

All containers, syringes, and needles that contain the vaccine should be disposed of in standard biohazard disposal containers immediately after use (Appendix G Handling of BCG Vaccine).

### 8.1.6 BCG Toxicity:

Adverse reactions are often localized to the bladder but may be accompanied by systemic manifestations. Systemic adverse effects such as malaise, fever, and chills often reflect hypersensitivity reactions that can be treated with antihistamines. The "flu-like" syndrome of 1-2 days' duration that frequently accompanies intravesical BCG administration often can be managed by standard symptomatic treatment. However, symptoms such as fever ≥38.5°C (101.3°F), or acute local reactions such as epididymitis, prostatitis, or orchitis, persisting longer than 48 hours, suggest active infection, and consideration should be given to multiple-drug antituberculosis therapy.

9 CONCOMITANT MEDICATIONS

9.1 Exclusionary Medications:

any of the following medications or treatments:

8.2.3 Placebo Dose:

masking procedure.

preservative-free saline.

## 568 569

567

## 570

## 571

## 572 573

## 574 575

## 576

## 577

## 578

## 579

## 580

## 581

## 582

## 583

## 584

## 585

## 587

## 588

## 589

## 590 591

## 592

## 593

# 594

# 595

# 596

## 597 598

## 599

## 600

## 601

602 603

## 604

605

- 606
- 607 608
- 609 610
- 611
- Rifampin

• Isoniazid\*

• Other antituberculosis therapies (e.g. Ethambutol, Pyrazinamide)

medications will be recorded on the Concomitant Medication Form.

- Anticoagulant therapy (e.g. Coumadin®) with the exception of low dose aspirin therapy.
- Steroids (low dose steroid nasal spray is permitted)

- 611 • Intravesical therapies (e.g. DMSO, Clorpactin, Heparin)
  - Pentosanpolysulfate (Elmiron®)

613 614 615

612

\*Isoniazid (INH) will only be given if the patient is withdrawn from the study, unblinded according to protocol (see section 11.4), and the determination is made that antituberculosis therapy is necessary.

617 618 619

620

616

## 9.2 Allowable Medications:

9.2.1 Antibiotics

621 622 623

624

625

626

627

628

If, during the course of the study, patients must be treated with antibiotics, the patients will be allowed to defer treatment until the course of the antibiotics has been completed, not to exceed ten days between treatments. If the course of antibiotic treatment cannot be completed in this timeframe, the patient should be discontinued from the study. If a patient experiences a fever greater than 38.5°C (101.3° F) for 12-24 hours, the investigator should consult with the Infectious Diseases consultant associated with the study site.

629 630 631

632

633

634

In the event that antibiotics are required for prophylaxis or treatment, penicillins, cephalosporins, and macrodantin are recommended. Other antibiotics may be used as clinically required, however, the following have been demonstrated to have activity against TICE® BCG and should be avoided UNLESS absolutely necessary: Quinolones (Cipro, Floxin, Noroxin, Levaquin), Doxycycline, and gentamycin.

635 636

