# **4.4 Study Endpoints**254

## 4.4.1 Primary Endpoint

The primary endpoint on which the comparative efficacy of BCG and saline will be evaluated is a combined endpoint with two components: the patient-reported global assessment of response and the use of IC medications during the follow-up period.

The global evaluation of improvement for the primary endpoint will occur at week 34 or withdrawal, whichever comes first, relative to IC symptoms at baseline via the question: "As compared to when you started the study, how would you rate your interstitial cystitis symptoms now?" A seven point scale centered at zero will be used: -3) markedly worse; -2) moderately worse; -1) slightly worse; 0) no change; +1 slightly improved; +2) moderately improved; and +3) markedly improved. Participants who answer either +2) moderately improved or +3) markedly improved on the global evaluation will be considered to have evidence of "clinical improvement"

The second component relates to changes (increase or addition) in the use of IC treatment medications from the level at which the patient was stabilized at the beginning of the study. Increased usage of pre-study IC medications or the initiation of new IC medications during the last four weeks of post-treatment follow-up (week 31 - 34 post-randomization) will cause the patient to be classified as a non-responder.

Use of *breakthrough* medications as described in Section 4.3.1 will be allowed **with the exception of narcotic analgesics.** New or increased use of narcotic analgesics during the last four weeks of post-treatment follow-up (week 31-34) will be considered equivalent to starting a new IC medication, and therefore, would cause the patient to be classified as a non-responder. In addition, any patient who requests narcotic analgesics for treatment of IC symptoms during the last four weeks of post-treatment follow-up will also be classified as a non-responder.

Therefore, patients will be considered to be "responders" for the primary endpoint if they fulfill both of the following two criteria:

1. Report "moderate" or "marked" improvement on the global assessment at 34 weeks.

2. Report no increase in pre-study IC medications, and no initiation of new IC medications, and no new or increased use of narcotic medications during the final 4 weeks of the follow-up phase.

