The proportion of responders in each treatment arm will be compared in an intent-to-treat analysis to evaluate the overall effectiveness of BCG. Criteria #1 and #2 must both hold for a patient to be considered a responder at 34 weeks; all other patients will be considered "non-responders" and included in denominators for evaluation of response rates between treatment arms. Specifically, participants who withdraw from the study for

any reason (e.g. adverse event or participant choice) prior to the primary endpoint, will be considered treatment non-responders for the primary endpoint.

299300301

298

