### 10.3.1 Treatment Visit I

756 757

The study coordinator or investigator will review any clinical problems or events occurring since last study contact and update the concomitant medications record with any changes in medication use.

759 760 761

762

763

764

765

766

758

**Safety Assessment**: Female patients will be asked the date of their last menstrual period. An assessment of current birth control methods will be performed and recorded in the patient's chart and Case Report Form (CRF), if appropriate. For women of child-bearing potential, if pregnancy is suspected, a repeat β-HCG pregnancy test will be performed. If a repeat pregnancy test is performed and the results are positive, treatment should be discontinued immediately and the patient should be discontinued from the study and the Clinical Center Stop Point or "STOP" CRF should be filled out.

767 768 769

770

771

Prior to administering the first study treatment, a urine specimen for biomarkers study and a urine specimen for analysis will be obtained via catheterization of the patient. An analysis of the urine specimen will be completed *before* administration of the study treatment

772 773 774

775

When it has been determined that treatment may proceed, the Pharmacy should be notified to prepare and deliver the test solution. The patient will then be prepared for the treatment procedure. The patient's temperature will be recorded *before* the instillation of the test solution.

When test solution has been received from the Pharmacy, the time of preparation should be checked on the label and a determination made that the product was prepared no more than two hours ago. If the product was prepared more than two hours ago, it should be returned to the Pharmacy and fresh product obtained. Instillation of study product will be performed as described in Protocol for the Administration of Study Agent (Appendix C).

Prior to dismissal, the patient will be given instructions regarding the next study visit and will be advised of the two follow-up telephone calls as described in Section 10.3.1.1. An information sheet (Appendix F Patient Instructions Post-Treatment) will be reviewed with the patient describing signs and symptoms of complications or side effects, which should be reported, and providing 24-hour contact information. The patient will be asked to take an oral temperature at bedtime on the night of treatment and again at bedtime on the following night.

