## 11.5 Management of Associated Adverse Events and Discontinuation of Treatment

The administration of the test product may be discontinued at the patient's request or by the investigator, based on clinical judgment. If the patient is withdrawn from the study and participation terminated, a Clinical Center Stop Point "STOP" CRF must be completed and all required assessments performed as indicated in Section 10.6.

Patients will be instructed to report any adverse event experienced after treatment without delay. In addition, the patients will be contacted by the study coordinator during each of the two days following each instillation. If a patient has a serious adverse event or toxicity which has been judged to possibly or probably be associated with BCG, the investigator should consult with the Infectious Diseases physician affiliated with the study site. Patients reporting febrile reactions may be managed according to the method of Lamm and co-workers (41).

If, during the course of the study, patients must be treated with antibiotics, the patients will be allowed to defer treatment until the course of the antibiotics has been completed, not to exceed ten days between treatments. If the course of antibiotic treatment cannot be completed in this timeframe, the patient should be discontinued from the study. If a patient experiences a fever greater than 38.5°C (101.3°F) for 12-24 hours, the investigator should consult with the Infectious Diseases consultant associated with the study site.

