1. Report "moderate" or "marked" improvement on the patient-reported global assessment at 34 weeks.

2. Report no increase in pre-study IC medications, and no initiation of new IC medications, and no new or increased use of narcotic medications during the final 4 weeks (weeks 31-34) of the post-treatment follow-up phase.

The proportion of "responders" in each treatment arm will be compared in an intent-totreat analysis to evaluate the overall effectiveness of BCG. Criteria #1 and #2 must both hold for a patient to be considered a responder at 34 weeks; all other patients will be considered "non-responders", and will be included in denominators for evaluation of response rates between treatment arms. Specifically, participants who withdraw from the study for any reason (e.g. adverse event or participant choice) prior to the primary endpoint determination at 34 weeks, will be considered treatment "non-responders."

1219 1220

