## 13.4 Intent-to-Treat Analyses and Missing Data

An *intent-to-treat* analysis, in which all available data on all randomized participants are included, will be used for the primary comparison of treatments. All attempts will be made to keep missing data to a minimum, and participants who withdraw from treatment, will be encouraged to continue on study in order to provide complete follow-up information. However, it is expected that up to 15% of the randomized participants may withdraw prior to the final assessment of response at 34 weeks. These participants will be included in the denominator for evaluation of the response rate defined for the primary endpoint. The characteristics at the time of randomization for those participants without complete follow-up will be examined; however, there will be limited statistical power to detect any but major differences between these participants and those with complete follow-up. In addition, in order to assess the potential biases introduced by differential withdrawal among treatment arms, a comparison of withdrawal rates and time to withdrawal will be included as an ancillary analysis to the primary endpoint comparison.

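### The antibiotic rule in 9.2.1 and 11.5 removes patients from the study, not only from instillations, against 13.4 and Appendix C, and so forces avoidable non-responses

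*Protocol*

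**What the plan says.** **The rule.** Sections 9.2.1 and 11.5 carry the same text. A patient who needs antibiotics may defer the instillation until the course ends, "not to exceed ten days between treatments". Otherwise: "If the course of antibiotic treatment cannot be completed in this timeframe, the patient should be discontinued from the study".

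**Retention.** Section 13.4 states that "participants who withdraw from treatment, will be encouraged to continue on study in order to provide complete follow-up information".

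**Scoring.** Section 4.4.1 says that those who leave the study "prior to the primary endpoint, will be considered treatment non-responders for the primary endpoint". Section 13.1 repeats this for "participants who withdraw from the study for any reason (e.g. adverse event or participant choice) prior to the primary endpoint determination at 34 weeks".

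**Schedule.** Sections 2 and 10.3 allow 6 days to 3 weeks between instillations and accept that some patients will receive fewer than six.

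**Urinary infection at an instillation visit.** Appendix C (part I.A, to which part I.B refers repeat visits without ongoing adverse effects) says to complete antibiotic therapy after a positive culture and then instil. It sets no ten-day limit and no exit from the study.

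**The concern.** An antibiotic course is a reason to postpone or stop live BCG. It is not a reason to stop observing the patient. By ending participation, the rule turns a treatment interruption into a study withdrawal, and the endpoint definition turns that withdrawal into a treatment failure. Scoring withdrawals as failures is a legitimate convention. The defect is that the protocol itself produces withdrawals that need not occur, for a reason that does not measure response to therapy. Scheduled safety and symptom follow-up ends as well, just after an infection serious enough to need prolonged antibiotics.

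Sites also receive conflicting instructions. A patient with a urinary infection found at an instillation visit is kept in under Appendix C but may have to leave under 9.2.1. The ten-day limit does not say whether it means the whole gap between instillations or the delay beyond the due date.

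**Working it through.** **1. Does the wording mean full exit?** Three places show that the protocol separates stopping treatment from leaving the study.
- Section 10.3.1, on pregnancy, names both steps: "treatment should be discontinued immediately and the patient should be discontinued from the study".
- Section 11.5 first allows the test product alone to be discontinued, then deals separately with a further case: "If the patient is withdrawn from the study and participation terminated".
- Appendix B has one form for the treatment stop point and another for the study stop point.

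The antibiotic rule uses the study wording, so it means exit.

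**2. Can the exit assessment rescue the outcome?** Section 4.4.1 says: "The global evaluation of improvement for the primary endpoint will occur at week 34 or withdrawal, whichever comes first". Section 11.6 asks for efficacy data at early termination. But responder criterion 1 requires the rating at 34 weeks, and the withdrawal rule overrides whatever is reported at exit. Neither provision changes the classification.

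**3. What is lost per patient removed in Phase 1?** Section 10.4 and Appendix B schedule contacts at weeks 14, 18, 22, 26, 30 and 34. That is six, of which three (18, 26, 34) are clinic visits with questionnaires. Week 34 also carries the last biomarker sample. Section 4.2 limits Phase 2 to non-responders who completed Phase 1 treatment and follow-up, so a removed patient appears to lose the open-label offer too.

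**4. Effect on the response rate.** The denominator is the planned arm size from section 13.2: 103 per arm before adjustment. This figure reproduces with the continuity-corrected two-proportion formula for 30% against 50%, two-sided 0.05 and 80% power. Then 103 × 1.20 × 1.05 = 129.8, rounded to 130 per arm. One removed patient who would have met both criteria lowers that arm's rate by 1/130 = 0.0077, or 0.77 points. A removed patient who would not have responded changes nothing.

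**5. Does the ambiguity in the ten days matter?** Take weekly instillations and an infection found at the next visit, day 7. Course lengths of 5, 7 and 10 days are assumptions. End day = 7 + course length.

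| Assumed course | End day | Total gap (limit day 10) | Added delay (limit 7 + 10 = day 17) | General maximum (day 21) |
|---|---|---|---|---|
| 5 days | 12 | exceeds | fits | fits |
| 7 days | 14 | exceeds | fits | fits |
| 10 days | 17 | exceeds | fits | fits |

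Read as a total gap, the rule leaves 10 − 7 = 3 days for antibiotics. The same patient stays or leaves depending on the reading, although every case lies within the general three-week interval. If the infection is urinary, Appendix C keeps the patient in under either reading. The table shows that the text can be applied in two ways. It says nothing about how often the limit is broken.

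**The case against.** **Frequency is unknown.** The protocol gives no rate of antibiotic courses that break the limit, and Appendix C covers at least urinary infections found at an instillation visit. The number affected may be very small. This stands.

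**Section 13.4 is not flatly contradicted.** It speaks of patients who withdraw from treatment, whereas 9.2.1 is a specific instruction for one circumstance. Section 13.4 also anticipates up to 15% withdrawal, keeps those patients in the denominator and compares withdrawal by arm. The clash is therefore with its retention policy. But comparing withdrawal rates does not supply a week-34 state that was never recorded.

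**Bias against BCG.** A reader might infer that BCG patients would be removed more often, since the package insert reports fever and irritative reactions. Those data come from bladder cancer patients, with mitomycin C as the comparator in the randomized study. Both arms here are catheterised at each instillation, and the protocol gives no antibiotic use by arm. The direction is not derivable.

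**Loss of power.** A reader might also apply removal rates to the planning figures. Equal removal of 2% to 10% would shrink the 20-point difference to 19.6–18.0 points (20 × 0.98 and 20 × 0.90). Those rates are invented, and section 13.1 sizes the trial on the composite endpoint, which already counts withdrawals as failures. No power shortfall follows.

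**Keeping such patients is not free.** Section 11.5 breaks the blind for a febrile reaction thought to be due to BCG, so some retained patients would give an unblinded self-rating at week 34. Section 9.1 permits isoniazid only after withdrawal from the study, and Phase 2 eligibility would need a decision. These points bear on the fix and do not defend the rule.

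**Conclusion.** The point holds as an internal inconsistency that affects how the primary endpoint is classified, and it should be fixed. Followed as written, 9.2.1 and 11.5 create avoidable study withdrawals, and 4.4.1 and 13.1 make each one a non-response that no exit assessment can reverse. For Phase 1 the cost is up to six contacts per patient removed, and 0.77 points in that arm for each one who would have responded, assuming 130 per arm. The total effect and its direction cannot be derived, and the sample size is not in question. The rule operates only between instillations. The same wording would cover Phase 2 instillations, where it affects follow-up but no primary comparison.

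**What to change.** In 9.2.1 and 11.5, replace discontinuation from the study with: *discontinued from further study instillations; all scheduled visits and the week-34 assessment continue*.

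In the same change:
- Align the ten-day limit with the three-week maximum interval and with Appendix C. If ten days is kept, state whether it is the total gap or the added delay.
- Make 9.1 consistent, by saying whether isoniazid and other antituberculosis therapy require withdrawal from the study or only from instillations.
- State whether patients stopped under this rule who are non-responders at week 34 may enter Phase 2.

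The cost is a few sentences and a few more completed visits. The visits and the separate stop forms already exist. Some retained febrile patients may have been unblinded under 11.5, so their week-34 ratings should be identifiable as such.

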## ICCTG Protocol #2 – Visit Schedule (Weeks) Phase I – Randomized, Double-Blind Study

## **APPENDIX B**

		ening sits	Treatment Phase 6 Treatments in 10 Weeks				Post-Treatment Follow-up Phase 24 Weeks (6 Months)								
			RX	RX	RX	RX	RX	RX	Phone Visit	Phone	Clinic	Phone	Clinic	Phone	Clinic
Event	B1 -4	B2 -1	1	2	3	4	5 *	6 *	(optional)	Visit	Visit 18	Visit 22	Visit 26	Visit 30	Visit 34
Week	-4	-1	1*	*	*	*	*	*	10, 11, or 12	14					
Visit Number	1	2	3	4	5	6	7	8	9	10	11	12	13	14	15
Consent Form	Χ														
Clinic Visit	Χ	Χ	Χ	Χ	Χ	Χ	Χ	Χ			Χ		X		Χ
Treatment Follow-Up Phone Call									~	~		~		*	
Day 1 Follow-up (PHNTP)			2	A		A									
Day 2 Follow-up (PHNTP)			*	A		A									
Patient Contact Information (PTCONT)	Χ														
Medical History (MED)	Χ														
Voiding Diary (VOID)		$X^3$									$X^3$		$X_3$		$X^3$
Demographics (DEMO)	Χ														
Eligibility Confirmation (ELIG)	Χ	Χ													
Randomization (RAND)		Х													
Patient's Daily Medication Diary (PTDIARY)	X 3	X 	X 	X 	$X_3$	X 	$X_3$	X 			X³				X 3
Medication Diary Record (CMED)		Х	Х	Х	Х	Х	Х	Х			Х				Х
Instillation/Dosing Information (DOSE)			Х	Х	Х	Х	Х	Х							
Adverse Event/Serious Adverse Event (AE)			Х	Х	Х	Х	Х	Х	Х	Х	Х	Х	Х	Х	Х
Contraceptive Use (DOSE and STVISIT)			Х	Х	Х	Х	Х	Х	Х	Х	Х	Х	Х	Х	Х
Unmasking Record (UNMASK) 															-
Treatment Stop Point I (TSTOPI) 								Χ							·
Study Stop Point I (SSTOPI) 															X
Patient Transfer (TRANS) 															
Study Close-out (STCL) 															X
Patient Close-out (PTCL) 															Х
SYMPTOM QUESTIONNAIRES:															
Baseline Symptoms (BSYM1&2)	Х	Х													
Follow-up Symptoms (FUSYM)								Χ			Х		Χ		Х
IC Symptom & Problem Index (SYMPROB)		Х						Х			Х		Х		Х
Health Status Questionnaire (SF36)		Х		1				Χ			Х		Χ		Х
MOS Sexual Functioning Scale (MOS)		Χ						Χ			Х		Х		X

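### The antibiotic rule in Sections 9.2.1 and 11.5 removes a patient from the study when stopping instillations would be enough, and so makes that patient a non-responder

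*Protocol*

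**What the plan says.** Protocol Section 9.2.1 lets a patient who needs antibiotics during the study postpone instillations until the course is finished, "not to exceed ten days between treatments". If the course "cannot be completed in this timeframe, the patient should be discontinued from the study". Section 11.5 repeats the rule in the same words.

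Section 4.4.1 states that participants who withdraw for any reason before the primary endpoint are "considered treatment non-responders for the primary endpoint". Section 13.1 repeats this: withdrawal "prior to the primary endpoint determination at 34 weeks, will be considered treatment" non-response. In both places these patients stay in the denominator.

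Three other parts of the protocol treat stopping treatment and leaving the study as different events:

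- Section 11.5 says "The administration of the test product may be discontinued" at the patient's request or on the investigator's judgment. It then deals separately with what happens "If the patient is withdrawn from the study and participation terminated".
- Appendix B lists "Treatment Stop Point I (TSTOPI" and "Study Stop Point I (SSTOPI" as two forms.
- Section 13.4 says that participants who stop treatment will be urged to stay in the study so that follow-up is complete. Sections 2 and 10.3 accept that some patients will receive fewer than six instillations.

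**The concern.** A long antibiotic course is a reason to withhold instillations. It is not a reason to stop observing the patient. By ordering study exit, the rule creates a withdrawal that need not occur, and the endpoint definition then turns it into a treatment failure.

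What is lost is an observed week 34 outcome in an intent-to-treat comparison, replaced by an imposed one. The patient's remaining scheduled symptom and safety assessments (phone and clinic visits through week 34, Section 10.4) are also replaced by a single termination assessment under Section 11.6.

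**Working it through.** The point is textual, so the check follows one patient through the sections.

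**1. Trigger.** The patient needs antibiotics during the instillation period and cannot finish them within the limit. The package insert in Appendix H says that antimicrobial therapy may interfere with BCG's effectiveness and that instillations should be postponed meanwhile. This supports withholding instillations and says nothing about follow-up.

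**2. Is study exit just loose wording for stopping treatment?** The text does not read that way. Section 11.5 separates the two events, Appendix B gives each its own form, and Section 10.3.1 names both when a pregnancy test is positive. A coordinator applying Section 9.2.1 as written would end the patient's participation.

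**3. Effect on the endpoint.** Suppose the patient is moderately improved at week 34, with no added or increased IC medication and no new or increased narcotic use in the last four weeks.

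- Under the current rule the patient has left the study and is a non-responder under Sections 4.4.1 and 13.1.
- If only instillations stop, both responder criteria are assessed at week 34 and the patient is a responder.
- A patient who missed the same number of instillations because of poor tolerability, which Sections 2 and 10.3 allow, stays in the study and is assessed in the second way.

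Two patients with the same exposure and the same week 34 state can therefore be scored differently, depending only on why the instillations were missed.

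**4. Does another provision rescue the patient?** Section 4.4.1 places the global assessment at week 34 or at withdrawal, whichever is earlier, and Section 11.6 asks for efficacy data at early termination. Neither overrides the explicit sentence that makes withdrawals non-responders.

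**5. Size.** The plan's own figure comes first. For 30% against 50%, two-sided alpha 0.05 and 80% power, the continuity-corrected formula gives 103 per arm, as in the Section 13.2 table. Exact Fisher power at 103 per arm is 0.811. With the stated inflation, 103 × 1.20 × 1.05 = 129.8, so 130 per arm and 260 in total. The stated figures reproduce.

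One would-be responder sent out by the rule lowers the observed rate in that arm by 1/130 = 0.77 percentage points. The documents give no estimate of how many antibiotic courses would overrun, or in which arm, so the total effect cannot be calculated.

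**The case against.** The strongest reply is that the exit is deliberate. The rule appears twice in the same words. In Section 11.5 it stands among the provisions for adverse events associated with treatment. The drafters imposed study exit elsewhere too: for pregnancy in Section 10.3.1, and for isoniazid in the footnote to Section 9.1. The composite endpoint also has an express rule for withdrawals, and Section 13.4 expects up to 15% of them, so nothing is left undefined. This much stands: counting withdrawals as failures is a legitimate choice, and a sponsor may have meant this one. It still gives no reason to end follow-up, because concern about antibiotics interfering with BCG is met by withholding instillations.

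Four stronger readings are tempting, and the documents do not support them.

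- *The rule contradicts Section 13.4.* That section only encourages patients to stay and names no antibiotic cases. A specific rule can coexist with it, so this is tension and not contradiction.
- *The trial loses power or is biased.* Any power figure would need an invented share of affected patients. Section 13.1 also bases the sample size on the composite outcome, in which withdrawals are already failures, so reducing the 30% and 50% rates again could count the same loss twice. Section 13.2 takes the 30% from earlier studies, so this is not settled either way. Nothing in the documents shows an imbalance between arms.
- *Ten days contradicts the three-week maximum in Section 10.3.* A stricter limit for antibiotic cases can sit inside a wider general one. The wording does not say from when the ten days run, but the correction does not depend on settling that. Counting from the last instillation would leave no deferral at spacings of ten days or more, and no starting point before the first instillation.
- *Appendix C, step I.A.7, contradicts the limit.* That step is written for the first-instillation visit, where no interval between treatments yet exists.

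**Conclusion.** The point holds as a minor matter of design. It is certain that both sections order study exit, and that Sections 4.4.1 and 13.1 then impose non-response regardless of week 34 status. The effect on the result is not known: 0.77 percentage points of an arm's rate per would-be responder removed, with an unknown number of patients and no known direction. The conclusion rests on reading the rule literally, which the protocol's own separation of the two events supports. No stated sample size, power or significance level is wrong.

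**What to change.** In Sections 9.2.1 and 11.5, replace the order to leave the study with: *discontinued from further study instillations and followed on study to the week 34 assessment*. Record the event on the Treatment Stop Point form, not the Study Stop Point form. The ten-day figure can stay, and the separate provisions for pregnancy and for antituberculosis therapy are untouched.

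The cost is one phrase in two places. The form already exists, and no patients or visits are added beyond those already scheduled to week 34. The trade-off is that a few patients who stopped treatment early remain in follow-up and may count as responders if they meet both criteria at week 34. That is consistent with an intent-to-treat comparison and with how the protocol already treats others who receive fewer than six instillations.
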